- 3.2.13 Participants with active autoimmune disease or history of autoimmune disease that might recur, which may affect vital organ function or require immune suppressive treatment including systemic corticosteroids, are excluded. These include but are not limited to participants with a history of immune related neurologic disease such as multiple sclerosis, autoimmune (demyelinating) neuropathy, Guillain-Barre syndrome, or myasthenia gravis; participants with a history of systemic autoimmune disease such as SLE, connective tissue diseases, scleroderma, inflammatory bowel disease (IBD), Crohn's, ulcerative colitis, or hepatitis; and participants with a history of toxic epidermal necrolysis (TEN), Stevens-Johnson syndrome, or phospholipid syndrome. These participants should be excluded because of the risk of recurrence or exacerbation of disease. Participants with vitiligo or endocrine deficiencies, including thyroiditis managed with replacement hormones such as physiologic corticosteroids, are eligible. Participants with rheumatoid arthritis or other arthropathies; Sjögren's syndrome; psoriasis controlled with topical medication; or participants with positive serology, such as antinuclear antibodies (ANA) or anti-thyroid antibodies, should be evaluated for the presence of target organ involvement and potential need for systemic treatment but should otherwise be eligible.
- 3.2.14 Participants are permitted to enroll if they have vitiligo, type I diabetes mellitus, residual hypothyroidism due to autoimmune condition only requiring hormone replacement, psoriasis not requiring systemic treatment, or conditions not expected to recur in the absence of an external trigger (precipitating event).

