5.5 Duration of Therapy

Duration of therapy will depend on individual response, evidence of disease progression and tolerance. In the absence of treatment delays due to adverse event(s), treatment may continue for 2 years or 35 cycles of therapy or until one of the following criteria applies:

- Disease progression in any participant who showed first radiologic evidence of progressive disease (PD) by RECIST 1.1 (see Section 11.1.4) and is deemed clinically stable, it is at the discretion of the investigator to continue treating the participant until progression is confirmed at least 4 weeks from the date of the first radiologic evidence of PD. Further details are described below.
- Intercurrent illness that prevents further administration of treatment
- Unacceptable adverse event(s) which include the following (see also section):
 - Any Grade 2 drug-related uveitis or eye pain or blurred vision that does not respond to topical therapy and does not improve to Grade 1 severity within the re-treatment period OR requires systemic treatment
 - Participants requiring > two dose delays for the same type of event should be removed from protocol
 - Any adverse event, laboratory abnormality, or intercurrent illness which, in the judgment of the investigator, presents a substantial clinical risk to the participant with continued study drug dosing
 - Any dosing interruption lasting >5 weeks, with the following exceptions:
 - Participants being tapered after high dose corticosteroids over one month followed by a two-week observation period will be allowed an additional two weeks to restart treatment (a maximum eight-week interruption).
 - Dosing interruptions >5 weeks that occur for non-drug-related reasons may be allowed if approved by the Investigator. Prior to re-initiating treatment in a participant with a dosing interruption lasting >5 weeks, the PI must be consulted.
 - Grade 2 pneumonitis requiring steroids.
 - Grade 3 or Grade 4 drug-related autoimmune or inflammatory events including uveitis, pneumonitis, diarrhea, colitis, neurologic adverse events, hypersensitivity reaction, or infusion reaction of any duration requires discontinuation except as noted below:
 - Any other grade 3 non-skin, drug-related AE lasting >7 days including fatigue.

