6.2 Pembrolizumab dosing delays

Participants should be carefully monitored for toxicity. If a treatment delay is required for pembrolizumab, treatment with Eribulin is allowed. Guidelines for dose interruption recommendations for pembrolizumab are shown in Table 4. If treatment with pembrolizumab is withheld permanently, participants are allowed to continue to receive eribulin therapy. Evaluation of possible AEs should occur early, with early withholding of drug, and appropriate treatment as indicated in the management tables and following event specific guidelines. In some cases, pembrolizumab may be resumed as per section 5.9

AEs associated with pembrolizumab exposure may represent an immunologic etiology. These immune-related AEs (irAEs) may occur shortly after the first dose or several months after the last dose of pembrolizumab treatment and may affect more than one body system simultaneously. Therefore, early recognition and initiation of treatment is critical to reduce complications. Based on existing clinical study data, most irAEs were reversible and could be managed with interruptions of pembrolizumab, administration of corticosteroids, and/or other supportive care. For suspected irAEs, ensure adequate evaluation to confirm etiology or exclude other causes. Additional procedures or tests such as bronchoscopy, endoscopy, skin biopsy may be included as part of the evaluation. Based on the severity of irAEs, withhold or permanently discontinue pembrolizumab and administer corticosteroids. Dose interruption and toxicity management guidelines for irAEs associated with pembrolizumab are provided in Table 4.1 to Table 4.9.

Table 4.1 Guidelines for dose interruption and toxicity management guidelines for immune-related AEs associated with pembrolizumab

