All other immune-related AEs	Intolerable/persistent Grade 2	Withhold	
 Based on type and severity of AE administer corticosteroids 	
 Ensure adequate evaluation to confirm etiology and/or exclude other causes
	Grade 3	Withhold or discontinue based on the type of event. Events that require discontinuation include and not limited to: Guillain-Barre Syndrome, encephalitis		

	Grade 4 or recurrent Grade 3	Permanently discontinue		
1. Withhold or permanently discontinue pembrolizumab is at the discretion of the investigator or treating physician. NOTE: For participants with Grade 3 or 4 immune-related endocrinopathy where withhold of pembrolizumab is required, pembrolizumab may be resumed when AE resolves to \leq Grade 2 and is controlled with hormonal replacement therapy or achieved metabolic control (in case of T1DM).				

Table 4.2 Pembrolizumab dose delay for non-immunologically mediated adverse events

ALL OTHER EVENTS*	Management/Next Dose for Pembrolizumab
\leq Grade 1	No change in dose
Grade 2	Hold until \leq Grade 1 OR baseline (exceptions as noted below); Evaluate and continue at investigator discretion
Grade 3	Stop pembrolizumab (exceptions as noted below)
Grade 4	Stop pembrolizumab
*Not Pembrolizumab related, or pembrolizumab related non-immunologically mediated Recommended management: As clinically indicated	

- Any grade 2 drug-related uveitis or eye pain or blurred vision that does not respond to topical therapy and does not improve to Grade 1 severity within the re-treatment period OR requires systemic treatment should result in protocol treatment discontinuation.
- Any adverse event, laboratory abnormality, or intercurrent illness which, in the judgment of the investigator, presents a substantial clinical risk to the participant with continued study drug dosing should result in protocol treatment discontinuation.
- Tumor pain or associated tumor flare does not require permanent discontinuation.
- Participants with any grade < 2 laboratory abnormality may continue study treatment at the discretion^[SEP] of the investigator. Any grade 3 or 4 drug-related laboratory abnormality or electrolyte abnormality, that can be managed independently from underlying organ pathology with electrolyte replacement, hormone replacement, insulin, or that does not require treatment **does not** require discontinuation.

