- Expected hematologic AEs which are related to eribulin will be managed per eribulin dose modification tables and do not require delay of pembrolizumab, see section 6.1

Table 4.3 Pembrolizumab dose delay for skin rash and oral lesions

Skin Rash and Oral Lesions	Management/Next Dose for Pembrolizumab
\leq Grade 1	No change in dose; * evaluate and continue at investigator discretion
Grade 2	Hold* until \leq Grade 1 or resolved. Evaluate and continue at investigator discretion

Grade 3	Hold* until \leq Grade 1; Evaluate and resume at investigator discretion at same dose level
Grade 4	Stop pembrolizumab.
*Participants with purpuric or bullous lesions must be evaluated for vasculitis, Steven-Johnson syndrome, TEN, and autoimmune bullous disease including oral lesions of bullous pemphigus/pemphigoid. Pruritus may occur with or without skin rash and should be treated symptomatically if there is no associated liver or GI toxicity. Note skin rash typically occurs early and may be followed by additional events particularly during steroids tapering.	

Table 4.4 Pembrolizumab dose delay for pancreatitis

Pancreatitis Amylase/Lipase	Management/Next Dose for Pembrolizumab
\leq Grade 1	Continue treatment at same level at investigator discretion.
Grade 2	Continue treatment at same level at investigator discretion if asymptomatic.
Grade 3	Hold until Grade < 2 . Resume at same dose level if asymptomatic. Participants who develop symptomatic pancreatitis or DM should stop pembrolizumab. .
Grade 4	Hold until Grade < 2 . Resume at same dose level if asymptomatic. Participants who develop symptomatic pancreatitis or DM should stop pembrolizumab. .
Participants may develop symptomatic and radiologic evidence of pancreatitis as well as DM and DKA. Lipase elevation may occur during the period of steroid withdrawal and with other immune mediated events or associated with colitis, hepatitis, and participants who have asymptomatic lipase elevation typically have self-limited course and may be retreated. For treatment management of symptomatic pancreatitis please follow the Hepatic Adverse Event Management Algorithm.	

Table 4.5 Pembrolizumab dose delay for nausea and vomiting

Other GI Nausea, Vomiting	Management/Next Dose for Pembrolizumab
\leq Grade 1	No change in dose.
Grade 2	Hold pending evaluation for gastritis duodenitis and other immune adverse events or other causes. Resume at investigator discretion.

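### For a recurrent Grade 3 immune-related skin or oral event, Table 4.1 stops pembrolizumab permanently while Table 4.3 lets it resume, and nothing says which table governs

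*Combined protocol and SAP*

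**What the plan says.** The pembrolizumab rules for skin events are spread over several places in the protocol.

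- **Section 6.2, opening text:** "Dose interruption and toxicity management guidelines for irAEs associated with pembrolizumab are provided in Table 4.1 to Table 4.9". No order of precedence among the tables is given.
- **Table 4.1, residual row for immune-related events not named elsewhere in that table:** withhold for "Intolerable/persistent Grade 2"; withhold or discontinue by type of event for Grade 3; permanently discontinue for "Grade 4 or recurrent Grade 3".
- **Table 4.3, skin rash and oral lesions:** at Grade 3, hold until Grade 1 or lower, then "Evaluate and resume at investigator discretion at same dose level". At Grade 4, "Stop pembrolizumab".
- **Table 4.3 footnote:** "Participants with purpuric or bullous lesions must be evaluated for vasculitis, Steven-Johnson syndrome, TEN, and autoimmune bullous disease". Oral lesions of the bullous diseases are included. The footnote states no action that follows a positive result.
- **Section 5.5:** discontinuation is required, with exceptions noted, for "Grade 3 or Grade 4 drug-related autoimmune or inflammatory events including uveitis, pneumonitis, diarrhea, colitis" and other listed events. Skin is not in that list, and the next rule, on other Grade 3 events, is confined to non-skin events. Separately, more than two dose delays for the same type of event remove the participant.
- **Section 5.8 and the text after Table 4.9:** Section 5.8 discontinues pembrolizumab after steroid-treated events of Grade 3 or higher. Both places let participants with Grade 3 thyroiditis or skin rash carry on as for Grade 2 events once resolved. The text after Table 4.9 also stops pembrolizumab after more than two delays.

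**The concern.** Two rules that both apply on the face of the document give opposite actions for the same event. A participant whose Grade 3 immune-related rash resolves, who restarts, and whose rash then returns at Grade 3 must stop permanently under one table and may be treated again under the other. Treating physicians could follow either table and be within protocol. What is at stake is mainly participant safety, and also consistent pembrolizumab exposure across participants. The pass mark of 9 of 19 per arm and the stated 91% power do not depend on it.

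**Working it through.** The check is mainly a comparison of text. Arithmetic enters only for the size.

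**1. Do both tables apply to an immune-related skin event?** Section 6.2 points to all nine tables for immune-related events. Table 4.1 names no skin event, so such an event falls in its residual row. That row is not reserved for events without a table of their own: it names Guillain-Barré syndrome and encephalitis, which Table 4.7 also covers. Where a table is meant for non-immune events only, its title says so (Table 4.2). Table 4.3 carries no such limit, and its footnote deals expressly with autoimmune disease. Both tables apply as written.

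**2. Do they agree, event by event?**

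| Event | Table 4.1 residual row | Table 4.3 | Agree? |
|---|---|---|---|
| First Grade 3 | Withhold or discontinue, by type | Hold, may resume | Yes, for ordinary rash |
| Recurrent Grade 3 | Permanently discontinue | Hold, may resume | **No** |
| Grade 4 | Permanently discontinue | Stop | Yes |

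**3. Do other rules resolve the recurrence?**

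- *Delay limits (Section 5.5 and the text after Table 4.9).* The first Grade 3 event is delay 1 and the recurrence is delay 2. The limits require more than 2, so they act at delay 3 at the earliest. Table 4.1 acts at the recurrence itself.
- *Steroid rule (Section 5.8).* New or worsening immune events during steroid treatment or taper require permanent discontinuation. This covers a flare during the taper, but not a recurrence after steroids have ended and pembrolizumab has been restarted.

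The conflict remains in the second situation.

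**4. Grade 3 oral or bullous lesion found autoimmune on the footnote's evaluation.** Three texts could apply:

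- Table 4.3 covers skin rash and oral lesions, so by default its Grade 3 row (hold, may resume) applies.
- Section 5.5, read literally, discontinues for Grade 3 drug-related autoimmune events.
- Section 5.8 discontinues after steroid-treated Grade 3 events, and its exception names skin rash only.

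Whether skin rash in that exception includes oral and bullous lesions is not stated. This is an ambiguity, weaker than the direct contradiction in step 2.

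**5. Size.** Inputs are from Section 2.6 (the breast cancer trial of the same combination) and the planned total of 57.

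- Grade 3-4 rash: 1.9%. Expected number: 0.019 × 57 = 1.08, about 1 participant.
- The denominator is inferred from that section's own counts: 24 / 0.224 = 107.1 and 34 / 0.318 = 106.9, so 107. Then 0.019 × 107 = 2.0 events. The exact (Clopper-Pearson) 95% interval for 2/107 is 0.2% to 6.6%, that is 0.002 × 57 = 0.1 to 0.066 × 57 = 3.8 participants.
- The documents give no recurrence rate. If a fraction r recurs at Grade 3, the expected number is 1.08 × r: 0.3 at r = 0.25, 0.5 at r = 0.5, and 1.1 at most.

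**The case against.** The best defence is that a table specific to skin displaces a general residual row, so Table 4.3 simply governs. That is a reasonable way to read a protocol, but this one does not say so, and the overlap of the residual row with Table 4.7 counts against it. The delay limits and the steroid rule mean that resumption is not unlimited. That stands, but it does not decide the first recurrence.

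A reader might infer more than the documents support, and on four matters the defence prevails.

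- **Resuming after any Grade 3 rash contradicts Section 5.5.** It does not. Section 5.5 allows exceptions, does not list skin, and limits its next Grade 3 rule to non-skin events. Section 5.8 says twice that treatment may go on after Grade 3 skin rash, and the text after Table 4.9 repeats it. Resumption after a first ordinary Grade 3 rash is consistently supported.
- **The tables conflict on tolerable Grade 2 rash.** Section 5.2.3 already requires non-hematologic toxicity to be at baseline or below Grade 2 on Day 1 of each later cycle, and pembrolizumab is given only on Day 1. Ongoing Grade 2 rash above baseline bars the dose whichever table is read.
- **Table 4.3 permits re-exposure after confirmed Stevens-Johnson syndrome or TEN.** It is silent, not permissive. Resumption is discretionary, Grade 4 already stops, and Section 5.5 and the notes to Table 4.2 stop treatment for any event that the investigator judges a substantial clinical risk. The documents give no grade for TEN. The grade-by-grade content of the Appendix B skin algorithm is not visible in the text reviewed, so it cannot be said that no action is stated anywhere.
- **Exclusion 3.2.13 forbids resumption.** Its reason, "These participants should be excluded because of the risk of recurrence or exacerbation of disease", shows the protocol's concern about recurrence, but the criterion governs entry and does not address retreatment on study.

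**Conclusion.** The contradiction on recurrent Grade 3 immune-related skin or oral events is real: permanent discontinuation under Table 4.1, possible resumption under Table 4.3, and no rule of precedence. The position of Grade 3 oral or bullous lesions found autoimmune is unclear for a related reason, the narrow wording of the skin rash exceptions.

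The number affected is small. About 1 of 57 participants would be expected to have Grade 3-4 rash, and fewer a recurrence, probably under one. This assumes that the breast cancer rate carries over to sarcoma. The figure is rough in both directions: it includes Grade 4, where the tables agree, and it counts the term rash alone, while Table 4.3 also covers oral lesions and other skin terms whose Grade 3 rates are not given. No effect on the 12-week endpoint is claimed. The point deserves correction because the two actions are opposite and bear on safety, not because many participants would meet it.

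**What to change.** State in Section 6.2 which table governs immune-related skin and oral events. Then reconcile Table 4.1, Table 4.3, Sections 5.5 and 5.8, and the text after Table 4.9 so that each of the following has exactly one action:

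1. a recurrent Grade 3 skin or oral event;
2. a Grade 3 event with a positive evaluation for Stevens-Johnson syndrome, TEN or autoimmune bullous disease.

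Say also whether skin rash in the exceptions includes oral and bullous lesions. The clinical team should choose the actions and check them against the Appendix B skin algorithm; this review takes no position on which rule is right. The cost is an edit to the tables, the footnote and a few sentences. The evaluation is already required, so no procedure is added, and neither the sample size nor the analysis changes.

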7. ADVERSE EVENTS: LIST AND REPORTING REQUIREMENTS

Adverse event (AE) monitoring and reporting is a routine part of every clinical trial. The following list of reported and/or potential AEs (Section 7.1) and the characteristics of an observed AE (Section 7.2) will determine whether the event requires expedited reporting **in addition** to routine reporting.

7.1 Expected Toxicities

7.1.1 Adverse Events Lists

7.1.1.1 Adverse Event Lists for Pembrolizumab

In the pembrolizumab monotherapy trials (P001/P002, P012, P013, and P028, plus the P011 monotherapy arm), the overall incidence of AEs ranged from 83.0% (73 of 88 participants in P012) to 100% (10 of 10 participants in P011). Not all the adverse events in the following list are all-inclusive and refer to the Pembrolizumab investigator brochure for a complete list.⁴⁸ The most commonly reported AEs included fatigue, diarrhea, decreased appetite, nausea, and anemia. The incidence of drug-related AEs (DRAEs) ranged from 39.8% (35 of 88 participants in P013) to 80.0% (8 of 10 participants in P011). The most commonly reported DRAEs across all studies were nausea, fatigue, and diarrhea. The incidence of Grade 3-5 DRAEs across studies ranged from 6.8% (6 of 88 in P013) to 12.0% (187 of 1562 participants) in P001/P002. The most commonly reported Grade 3-5 DRAEs were anemia, alanine aminotransferase increased, and aspartate aminotransferase increased. Most participants who experienced an AE continued in the study, with the incidence of AEs leading to discontinuation ranging from 1.9% (8 of 430 participants in P028) to 12.3% (192 of 1562 participants in P001/P002). The majority of AEs leading to discontinuation were not considered drug-related. Discontinuations due to a DRAE were infrequent and ranged from 0% (no participants in P011) to 4.5% (4 of 88 participants in P013). The most commonly reported DRAEs leading to discontinuation were pneumonitis, alanine aminotransferase increased, and aspartate aminotransferase increased.

List of AEs considered expected:

- Endocrine disorders: Adrenal insufficiency, Hyperthyroidism, Hypophysitis, Hypopituitarism, Hypothyroidism, Secondary adrenal insufficiency, Thyroid disorder
- Eye disorders: Uveitis
- Gastrointestinal disorders: Abdominal pain, Colitis, Diarrhea, Pancreatitis
- General disorders and administration site conditions: Asthenia, Pyrexia

- Hepatobiliary disorders: Autoimmune hepatitis, Hepatitis
- Infusion related reaction
- Metabolism and nutrition disorders: Diabetic ketoacidosis, Hyponatremia, Type 1 diabetes mellitus
- Musculoskeletal and connective tissue disorders: Arthralgia, Back pain, Myositis
- Nervous system disorders: Guillain-Barré syndrome
- Renal and urinary disorders: Nephritis
- Respiratory, thoracic and mediastinal disorders: Cough, Pneumonitis
- Skin and subcutaneous tissue disorders: Pruritus, Rash, Severe skin reaction, Vitiligo

7.1.1.2 Adverse Event Lists for Eribulin

Not all the adverse events in the following list are all-inclusive and refer to the Eribulin investigator brochure for a complete list.⁶⁴ Most AEs on studies with eribulin are grade 1 or 2. Peripheral neuropathy was an important AE leading to discontinuation of therapy. The most common adverse reactions ($\geq 25\%$) reported in participants receiving eribulin on the eribulin versus dacarbazine phase II trial in soft tissue sarcomas were fatigue, nausea, alopecia, constipation, peripheral neuropathy, abdominal pain, and pyrexia. The most common ($\geq 5\%$) grade 3 to 4 laboratory abnormalities reported in participants receiving eribulin were neutropenia, hypokalemia, and hypocalcemia. The most common serious adverse reactions reported in participants receiving eribulin were neutropenia (4.9%) and pyrexia (4.5%). The most common adverse reactions resulting in discontinuation of eribulin were fatigue and thrombocytopenia. 26% of participants required at least one dose reduction. The most frequent adverse reactions that led to dose reduction were neutropenia (18%) and peripheral neuropathy (4%).

The most frequently reported eribulin -related AEs were:

- Asthenia/fatigue (all grade 62%)
- Alopecia (all grades 35%)
- Urinary Tract Infection (all grades 11%, grade 3 to 4 2.2%)
- Neutropenia (all grades 63%, grade 3 to 4 32%)
- Nausea (all grade 41%)
- Anemia(all grades 70%, grade 3 to 4 4.1%)
- Pyrexia(all grades 28%, grade 3 to 4 0.9%)
- Leucopenia
- Anorexia(all grade 19%)
- Constipation(all grades 32%, grade 3 to 4 0.9%)
- Abdominal Pain (all grades 29%, grade 3 to 4 1.8%)
- Stomatitis (all grades 14%, grade 3 to 4 0.9%)
- Vomiting(all grade 19%)
- Diarrhea (all grade 17%)

- Headache (all grades 18%, grade 3 to 4 0%)
- Peripheral Edema (all grade 12%)
- Cough (all grade 18%)
- Back Pain (all grade 16%)
- Arthralgia/Myalgia (all grade 16%)
- Peripheral neuropathy (all grades 29%, grade 3 to 4 3.1%)
- Increased ALT (all grades 43%, grade 3 to 4 2.3%)
- Increased AST (all grades 36%, grade 3 to 4 0.9%)
- Hypokalemia (all grades 30%, grade 3 to 4 5.4%)
- Hypocalcemia (all grades 28%, grade 3 to 4 5.0%)
- Hypophosphatemia (all grades 20%, grade 3 to 4 3.2%)

Less common adverse reactions ($\geq 5\%$ to $< 10\%$) included thrombocytopenia, increased lacrimation, dyspepsia, hyperglycemia, muscle spasms, musculoskeletal pain, dizziness, dysgeusia, insomnia, anxiety, hypotension, and oropharyngeal pain.

